5. A positive urine drug screen for cocaine, amphetamines, methamphetamines, benzodiazepines, PCP, methadone, barbiturates, marijuana, ecstasy (MDMA), oxycodone, tricyclic antidepressants, and opiates (low level cut-off 300 ng/mL) during any session.

Psychiatric Exclusion (as determined by self-report on phone screen, through MINI, and/or the Columbia Suicide Severity Rating Scale (C-SSRS) during Intake):

1. Current psychiatric disorders (depression, bipolar, schizophrenia, hypomanic/manic episode) as determined by self-report and/or MINI psychological interview.
2. Past history of psychiatric disorders (including suicide attempt) other than depression as determined by self-report and/or MINI psychological interview.
3. Suicide risk score on MINI greater than 1.
4. Current (past month) suicidal ideation or lifetime suicidal behavior on the C-SSRS.

Medical:

1. Females who are currently pregnant, planning a pregnancy during the study, or currently breastfeeding/lactating. All female subjects shall undergo a urine pregnancy test at the Intake and must agree in writing to use an approved method of contraception. Following enrollment, pregnancy tests will be conducted at the end of each baseline week.
2. For those with a history of jaundice/liver disease: liver function tests more than 20% outside of the normal range and/or Gamma-glutamyl Transpeptidase (GGT) values more than 20% outside of the normal range. If Albumin/Globulin ratios are 20% outside of normal range the abnormal value will be evaluated for clinical significance by the Study Physician and eligibility will be determined on a case-by-case basis.
3. Heart/Cardiovascular disease (e.g., angina, coronary heart disease, stroke, etc.) in the past 6 months.
4. Endocrine or metabolic disorders (e.g., Type-I diabetes).

5. Blood disorders (e.g., anemia or hemophilia).
6. Uncontrolled hypertension (BP systolic greater than 159 and/or diastolic greater than 99)*.
7. Clinically significant dyssomnia (except insomnia; e.g. sleep apnea syndrome, narcolepsy) [25, 26].

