* Participants presenting with SBP greater than 159 mmHg and/or DBP greater than 99 mmHg at the Intake visit will be instructed to sit quietly for 10 minutes. Then the participant will have a second blood pressure reading taken after a 10 minute period. If, after the second reading the SBP greater than 159 mmHg and the DBP greater than 99 mmHg, the individual will be instructed to sit comfortably for 10 minutes and then have a third blood pressure reading. If, after the third reading the SBP greater than 159 mmHg and the DBP greater than 99 mmHg, the individual will be ineligible to participate.

Medication:

1. Current use or recent discontinuation (within the past month) of any of the following medications:
 - a. Anti-anxiety or panic disorder medications (e.g., clonazepam, alprazolam).
 - b. Anti-psychotic medications (e.g., thiorazine, Seroquel).
 - c. Mood-stabilizers (e.g., Lithium, Lamictal/lamotrigine, valproic acid, Neurontin/gabapentin, Topamax/topiramate, Tegretol/carbamazepine).
 - d. Prescription stimulants (e.g., Provigil, Ritalin, Adderall).
 - e. Medications contraindicated with ramelteon (e.g., fluvoxamine, donepezil, doxepin, buprenorphine or other medications metabolized by certain cytochrome P450 enzymes)
 - f. Hormonal birth control that contains ethinyl estradiol
 - g. Other medications containing ethinyl estradiol
2. Current use or recent discontinuation (within the past 2 weeks) of any of the following medications (subjects must agree to refrain from using any other sleep aids while enrolled in the study):
 - a. Sleep medications (e.g., zolpidem/Ambien, eszopiclone/Lunesta) [25, 26]
 - b. Over-the-counter sleep aids (e.g., melatonin, diphenhydramine/Benadryl)
3. Daily use of opiate-containing medications for chronic pain (Duragesic/fentanyl patches, Percocet, Oxycontin). Smokers who report taking opiate-containing medications on an “as-needed” basis will be instructed to refrain from use until their study participation is over and informed that they will be tested to ensure they have complied with this requirement.
4. Known allergy to study medication (e.g., angioedema).

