Blood Pressure. At the Intake, participants presenting with elevated blood pressure (i.e., systolic blood pressure greater than 159 and/or diastolic blood pressure greater than 99) will have a second blood pressure reading taken after a ten minute period in which the participants will be instructed to sit comfortably. If, after the second reading the SBP is greater than 159 mmHg and/or the DBP is greater than 99 mmHg, the individual will be instructed to sit comfortably for 10 minutes and then have a third blood pressure reading. If, after the third reading the SBP is greater than 159 mmHg and/or the DBP is greater than 99 mmHg, the individual will be ineligible to participate.

Blood pressure will be measured at all subsequent in-person visits. If participants present with elevated blood pressure (i.e., systolic blood pressure greater than 159 mmHg and/or diastolic blood pressure greater than 99 mmHg) at any subsequent visit, the staff will follow the same steps listed above. If, after a third reading, systolic blood pressure remains greater than 159 mmHg and/or diastolic remains greater than 99 mmHg, the subject will be told to not take the next dose of study medication. If a participant presents with a SBP between 151-159 mmHg and/or DBP between 91-99 mmHg at the Intake or any visit during a Baseline week, the research staff will inform the participant that they have mild, Stage I, hypertension and advise they consult with a physician. The participant will remain eligible for the study and receive nicotine patches as scheduled. The research staff will notify the Study Physician/Health Care Provider who will review the blood pressure reading and determine whether it is safe for the subject to continue. Research staff will follow up with the participant accordingly.

Liver Function Tests and Gamma-glutamyl Transpepsidase. Only individuals with a history of jaundice/liver disease will provide a blood sample for liver function tests. One 8.5ml blood sample will be drawn at the Intake visit to conduct liver function tests. Blood will be collected and placed in a serum-separator tube (SST) and mixed thoroughly. Samples will be centrifuged at 3000 rpm for 15 minutes. The following chemistry will be assessed:

1. Total protein.
2. Albumin.
3. Globulin.
4. Albumin:Globulin ratio.
5. Bilirubin (total, conjugated and unconjugated)
6. Aspartate amino transferase (AST).
7. Alanine amino transferase (ALT).
8. Alkaline phosphatase (AP).

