Transdermal Nicotine (TN) Replacement Therapy: All participants will receive transdermal nicotine (TN) patch therapy to aid in quitting smoking. This therapy is available over the counter and is very well tolerated. Participants will use the 21 mg patch for 5 days during each quit assessment week. Nausea, vomiting, weakness, dizziness, and rapid heartbeat occur rarely and are most often caused by continuing to smoke while using the patch. In addition, there is a risk of peptic ulcer formation and delayed wound healing associated with nicotine replacement therapies. Some individuals who use the patch experience minor skin irritation, such as redness, rash, or minor swelling, and insomnia and dream abnormalities. Because sleep problems are a primary mechanism of interest, participants will be instructed to remove the patch during the night while sleeping to avoid dream abnormalities. All of these reactions cease once the patch is removed.

During the third visit of each baseline week (weeks 1 and 5), a member of the research staff will review the purpose of using the nicotine patch (e.g., to help manage withdrawal symptoms; not a substitute for behavioral quitting strategies), provide directions on how to use the patch (e.g., abstinence from smoking, patch location, time, activity, and potential skin reactions), and answer any questions.

Because increased blood pressure is a side effect of TN patch therapy, blood pressure will be closely monitored at each visit. Expanding the upper limit of the blood pressure to less than 160/100 does not increase the risk to subjects enrolled in this trial. The risk of increased blood pressure is no greater than the risk from smoking and quitting smoking will lower an individual's risk. If a participant presents with a SBP between 151-159 mmHg and/or DBP between 91-99 mmHg at the Intake or Pre-Quit visit, the research staff will inform the participant that they have mild, Stage I, hypertension and advise they consult with a physician. The participant will remain eligible for the study and receive nicotine patches as scheduled.

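### The Intake footnote to the blood-pressure exclusion requires both limits to be exceeded on repeat readings, where the criterion and the procedure section require only one

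*Combined protocol and SAP*

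**What the plan says.** The protocol states the Intake blood-pressure rule in several places.

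- **Key Exclusion Criteria, Medical, criterion 6:** "Uncontrolled hypertension (BP systolic greater than 159 and/or diastolic greater than 99".
- **Footnote to criterion 6, first reading:** "Participants presenting with SBP greater than 159 mmHg and/or DBP greater than 99 mmHg at the Intake visit will be instructed to sit quietly".
- **Footnote, second reading:** "If, after the second reading the SBP greater than 159 mmHg and the DBP greater than 99 mmHg, the individual will be instructed" to rest and be measured a third time.
- **Footnote, third reading:** "If, after the third reading the SBP greater than 159 mmHg and the DBP greater than 99 mmHg, the individual will be ineligible".
- **Section 3.1, Blood Pressure, Intake:** the same three-reading sequence with *and/or* throughout. Its last step begins "If, after the third reading the SBP is greater than 159 mmHg and/or the DBP is greater than 99 mmHg, the individual" and ends in ineligibility.
- **Section 3.1, Blood Pressure, later visits:** the same *and/or* limits. If they are still exceeded at a third reading, "the subject will be told to not take the next dose of study medication".
- **Potential Study Risks, Transdermal Nicotine:** "Expanding the upper limit of the blood pressure to less than 160/100 does not increase the risk to subjects enrolled in this trial".

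The Intake entry under Study Visits tells staff to confirm eligibility against the listed inclusion and exclusion criteria. Its blood-pressure item refers them to the procedure in section 3.1.

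**The concern.** The footnote is tied to criterion 6 by an asterisk and reads as its working instruction. It opens with the criterion's *and/or*, then switches to *and* at the two steps that decide whether a person is measured again and whether that person is excluded. Someone with persistent isolated systolic or isolated diastolic hypertension therefore meets criterion 6 but is not made ineligible by the footnote beneath it.

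This is a safety limit. Every participant wears a 21 mg patch in both quit weeks, and the risk section says: "Because increased blood pressure is a side effect of TN patch therapy, blood pressure will be closely monitored at each visit". Apart from those awaiting liver tests, eligible participants are randomized at Intake, so Intake is the main gate. A person admitted in error can still be picked up later, but the later-visit rule leads to a held dose and not to ineligibility. Missing two or more doses is itself a listed exclusion (General Exclusion, item 7), so a screen failure could become a loss after randomization. That last step is an inference from the two rules; the protocol does not say it.

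**Working it through.** The protocol gives no figure to reproduce. The check compares the two texts and enumerates what each one excludes.

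**Inputs.** Limits: systolic (SBP) above 159, diastolic (DBP) above 99 mmHg, the same in all places. Connectives at Intake:

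| Step | Criterion 6 | Footnote | Section 3.1 |
|---|---|---|---|
| First reading | *and/or* (no steps given) | *and/or* | *and/or* |
| Second reading | – | *and* | *and/or* |
| Third reading, ineligible | – | *and* | *and/or* |

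**Persistent readings.** Take the same value at all three measurements.

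| Reading | Literal footnote | Section 3.1 |
|---|---|---|
| 165/105 | excluded | excluded |
| 165/85 | not excluded | excluded |
| 140/105 | not excluded | excluded |
| Neither limit exceeded | not excluded | not excluded |

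In the second and third rows the footnote triggers a second reading. The *and* condition then fails, so no third reading is called for and no exclusion follows.

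**All patterns.** Class each reading as neither limit exceeded, SBP only, DBP only, or both. Three readings give 4 × 4 × 4 = 64 patterns.

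- Section 3.1 excludes when every reading is in one of the three raised classes: 3 × 3 × 3 = 27.
- The literal footnote excludes when the first reading is in any raised class and the second and third are both in the class *both*: 3 × 1 × 1 = 3.
- All 3 are among the 27. Excluded by section 3.1 but not by the footnote: 27 − 3 = 24. Excluded by the footnote but not by section 3.1: 0.

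The procedure stops early once a reading is acceptable, so not all 64 patterns are observed in practice. Under section 3.1 the observable sequences number 1 + 3 + 36 = 40; under the literal footnote, 1 + 9 + 12 = 22. The excluded counts of 27 and 3 are unchanged, because an excluded person always has three readings.

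**Which wording is intended.** Criterion 6 and section 3.1 both state *and/or* for exclusion. The footnote's own first sentence and the 160/100 ceiling in the risk section are consistent with that. Nothing in the protocol gives a reason to require both limits on repeat readings.

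**After the fix.** With *and/or* at the second and third steps, the footnote excludes the same 27 patterns as section 3.1, and all four rows of the persistent-reading table agree.

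**The case against.** The strongest reply is that the footnote gives one sufficient condition for ineligibility and never says that a person over a single limit is eligible. Criterion 6 still applies, so the protocol taken as a whole excludes the person at 165/85. That is a fair reading of the whole document, and it is why this is a contradiction to be corrected and not a wrong threshold. It does not rescue the footnote, which a staff member could follow step by step and stop after the second reading.

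The safeguards are real. The Intake blood-pressure item points to the correct text in section 3.1. A medical professional leads a physical examination at Intake. The Project Manager, the principal investigator and the Study Physician confirm eligibility together, and chart review covers the blood-pressure forms (section 4.1). Pressure is measured at all three Baseline visits, before any patch is worn. The risk section also lets the Study Physician reduce or stop the patch when side effects occur.

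These points limit the likely harm, but they do not fully replace the Intake gate:

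- The later-visit rule withholds study medication without naming the patch, which the protocol elsewhere lists separately.
- The provision for adjusting the patch deals with reactions to it, not with hypertension that was already present.
- The sentence on physician review follows the text on the mild range (151–159 and/or 91–99), and it is not clear that it covers higher readings.

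Two smaller objections also stand in part. A retest trigger may properly be wider than an exclusion rule, so the footnote's first sentence is only supporting evidence; criterion 6 and section 3.1 carry the argument. The pattern count shows the direction and extent of the logical conflict and says nothing about how many people are affected.

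**Conclusion.** The concern holds. The footnote contradicts criterion 6 and section 3.1 and, read literally, does not exclude persistent isolated systolic or isolated diastolic hypertension. It excludes 3 of the 27 patterns that section 3.1 excludes, and it never excludes anyone whom section 3.1 would admit. The conflict is confined to Intake, since the later-visit rules already use *and/or*.

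The count assumes the four-way classification of each reading and gives patterns no weights. The protocol reports no blood-pressure distribution, so the number of people affected cannot be estimated. It is probably small if staff follow the pointer to section 3.1, and nil if they always do. This is an internal inconsistency with no bearing on sample size, power or the analysis. It should still be corrected, because it sits in an operative safety criterion and costs almost nothing to put right.

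**What to change.** In the footnote to criterion 6, change *and* to *and/or* in the second-reading sentence and again in the third-reading sentence, so that both match criterion 6 and section 3.1. The later-visit rules in section 3.1 need no change for this point.

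Check the Intake blood-pressure forms of anyone already enrolled for repeat readings that exceeded only one limit, and refer any such case to the Study Physician.

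The cost is two connectives in one footnote plus that one-off check of existing records. No visit or procedure is added. There may be a few more screen failures at Intake, and none where staff already follow section 3.1.

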 7. Mood, smoking urges, withdrawal symptoms, sleep measures

At the last visit of the first Quit Assessment Week (Week 2), the SensewearPro® armband and charger will be collected from the participant, as he or she will not be using the SensewearPro® armband during the washout period. If the participant continues the study, the participant will receive the SensewearPro® armband at their first visit of the second Baseline Week (Week 5).

These sessions can be scheduled for any time of day. Ideally, the subsequent sessions would be at the same time of day, but can be scheduled up to 3 hours earlier or later. However, the sessions may go beyond 3 hours as determined by PI discretion.

At the final visit of the study, participants will be offered information (i.e. flyer, brochure, etc.) about a smoking cessation research program at the CIRNA. If no cessation studies are available or the participant does not wish to participate, they will be provided a list of referrals to other cessation programs in the greater Philadelphia area (e.g., the Comprehensive Smoking Treatment Program at UPenn Presbyterian). The participant's decision whether or not to receive this information will be documented. Participants will return the SensewearPro armband and will be given a summary report of their physical activity and sleep patterns.

- Washout Weeks (Weeks 3 and 4): During these two weeks, participants will not have any study visits or take any study medication. They will be instructed to smoke *ad libitum*. Subjects who abstain during week 2 will be required to resume smoking during week 3 to remain in the study. Subjects will be told that they may withdraw from the study if they choose not to resume smoking. We expect few subjects to discontinue the study for this reason [4, 35, 36].

3. Description of Measures and Variables

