Breath Alcohol Concentration. The breath alcohol concentration (BrAC) assessment will be administered at the Intake visit and all subsequent study visits. The breath alcohol monitor assesses expired breath for alcohol content. A reading greater than or equal to 0.01 at any session indicates alcohol consumption within the last 14 hours and will result in the participant being withdrawn from the study.

Activity (Week #)	Intake	Baseline (1 & 5)			Quit Assessment (2 & 6)				
Day	0	Mon	Wed	Fri	Mon	Tue	Wed	Thu	Fri
TREATMENT									
Ramelteon (RAM) or Placebo					X ^a	X ^a	X ^a	X ^a	X ^a
Transdermal Nicotine (TN)					X	X	X	X	X
SCREENING/COVARIATES									
Demographics	X								
Smoking History/FTND	X								
Medical/ ETOH History (self-report)	X								
Psychiatric History (Self-report and MINI)	X								
Suicidal Behavior/ Ideation (C-SSRS)	X								
Urine drug/pregnancy screen	X			X					
Breath alcohol	X	X	X	X	X	X	X	X	X
Blood pressure	X	X	X	X	X	X	X	X	X
Blood draw (liver function tests) ^b	X								
Brief counseling				X					
TREATMENT VARIABLES									
Concomitant Medication Review	X	X	X	X	X	X	X	X	X
RAM Adherence (pill count)					X	X	X	X	X
TN Adherence					X	X	X	X	X
Side Effects (TN and RAM)		X	X	X	X	X	X	X	X
INTERMEDIATE OUTCOMES									
Sleep Diary		X	X	X	X	X	X	X	X
Pittsburgh Sleep Quality Index (PSQI)		X	X	X	X	X	X	X	X
Sleep efficiency (SensewearPro)		X	X	X	X	X	X	X	X
Depression Symptoms (CESD)	X			X					X
Withdrawal, Craving, Affect		X	X	X	X	X	X	X	X
SMOKING OUTCOMES									
Cessation/Smoking Rate (TLFB)	X	X	X	X	X	X	X	X	X
Carbon Monoxide (CO) Test	X	X	X	X	X	X	X	X	X
Note. No visits or assessments during washout (weeks 3-4). FTND=Fagerstrom Test for Nicotine Dependence; CESD= Center for Epidemiological Studies on Depression; TLFB=Timeline Followback a study medication taken the previous night; b only for those with a history of jaundice/liver disease									

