3.4 Smoking Outcomes

Smoking Rate (TLFB). We will assess the number of cigarettes smoked on each day throughout the study. A standard timeline follow-back (TLFB) method will be used [67], as we have done previously [68] to assess self-reported smoking rate. During each quit week, abstinence will be assessed daily by self-report of no smoking at all over the prior 24 hours and an expired-air CO less than 5 ppm (except for the Monday visit when CO may be less than 10ppm or less than 50% Baseline CO). This stringent biochemical criterion for validating smoking cessation has been shown to be more sensitive to detect smoking and specific to verify abstinence than higher CO cut-offs [69].

Carbon Monoxide. Carbon monoxide (CO) measures will be made using a Vitalograph Breath CO Analyzer (McNeil International, Inc., Lenexa, KS). The manufacturer will have calibrated this device within the past year. A new, disposable cardboard mouthpiece will be provided for each participant. The device has a digital screen which reports CO levels in parts per million (ppm). Participants will be asked to provide a CO breath sample by taking a large breath then exhaling twice. Then, they will take another deep breath and hold their breath for 10 seconds, as per the recommendations of the American Thoracic Society. Then, when instructed to do so, participants will exhale as forcefully and as long as they are comfortably capable. The largest value displayed is recorded during all CO breath samples. CO breath samples will be collected at each study visit. At the Intake, participants must have CO readings greater than or equal to 10ppm in order to be eligible for the study.

2. Statistical Analysis

Sample size.

Effect sizes for power analyses were derived from prior work on TN effects on days of abstinence (Aim 1) [6], studies demonstrating RAM's effects on sleep (Aim 2), and our preliminary data. All significance levels will be set at 0.05. Our primary hypothesis is that RAM will increase the number of days abstinent (out of 5), compared to placebo. In prior validation work, the average number of days abstinent for TN was 2.0 ± 0.3 [6]. Fifty subjects provide 80% power to detect a difference of 0.55 days between RAM and PLA, using a SD of 1.36 and a within-subjects correlation of 0.78 [31].

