For Aim 2, meta-analyses indicate that RAM is associated with reducing SOL by 4.3 min and increasing sleep efficiency by 4.42% [70]. Our preliminary data suggest that TN increases sleep disturbance by 58% ($d=0.28$) in abstinent smokers and that abstinence increases SOL by ~5 min and decreases sleep efficiency by ~5%. Fifty subjects provide 80% power to detect differences of 6 min in SOL and 5% in sleep efficiency between RAM and PLA, using a within-subject correlation between 0.4 and 0.8. Thus, Aims 1 and 2 are sufficiently powered.

Statistical Analysis.

For Aim 1 (H1), a within-subject ANOVA will test the primary hypothesis for effects of RAM (vs. PLA) on number of days abstinent during the quit week.

For Aim 2 (H2a), separate 2 drug (RAM vs. PLA) x 2 week (baseline vs. quit week) repeated measures ANOVAs will test the effects of RAM on SOL and sleep efficiency. Drug and week are within-subject factors and sleep measures will be averaged across days within each baseline and quit week. We are primarily interested in the drug x week interaction to test whether RAM (vs. placebo) attenuates sleep disturbance during the quit week, relative to baseline. Thus, each period has its own baseline control comparison. A supplemental analysis will include only days during the quit week when subjects are abstinent.

For Aim H2b, linear regression models will test whether sleep disturbance predicts number of days abstinent and

whether this relationship varies by treatment. Models will include covariates (e.g., baseline depression/anxiety, FTND, sex, and age). We will also examine correlations between sleep disturbance data and nicotine withdrawal and depression/anxiety symptoms in both groups.

3. Confidentiality

All participant information will be kept in a secure filing cabinet that is accessible only to authorized study personnel. All study databases containing participant information will be password protected, and accessible only to authorized study personnel. Any study communications made by e-mail will use ID numbers and not include names or other personal information. All data sets will use ID numbers only.

How will confidentiality of data be maintained? Check all that apply.

- Paper-based records will be kept in a secure location and only be accessible to personnel involved in the study.
- Computer-based files will only be made available to personnel involved in the study through the use of access privileges and passwords.

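### Resumed smoking after period 1 is required but not defined or checked, and H1 ignores baseline smoking, so carry-over that differs by first drug could dilute the ramelteon effect

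*Combined protocol and SAP*

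**What the plan says.** The trial is a randomised, counterbalanced two-period crossover. Each period has a week of free smoking followed by a quit week, with weeks 3 and 4 as washout.

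For the washout, section 2 (Study Visits) states: "Subjects who abstain during week 2 will be required to resume smoking during week 3 to remain in the study". It gives no amount of smoking and no method of verification. The note to the schedule table in section 3.1 reads "No visits or assessments during washout (weeks 3-4". In week 5, CO and timeline follow-back (TLFB) cigarette counts are taken at all three visits, but no level is attached to either. The one CO floor for smoking status is at entry (section 3.4, Carbon Monoxide): "At the Intake, participants must have CO readings greater than or equal to 10ppm in order to be eligible for the study".

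A quit-week day counts as abstinent when the participant reports no smoking and CO is below 5 ppm. On Monday, CO below 10 ppm, or below half the baseline-week reading, is enough. Each confirmed day pays $10.

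For the primary hypothesis (Statistical Analysis, Aim 1), "a within-subject ANOVA will test the primary hypothesis for effects of RAM (vs. PLA) on number of days abstinent during the quit week". No baseline-smoking, period or sequence term is named. For the sleep outcomes under H2a, by contrast, the plan says: "Thus, each period has its own baseline control comparison".

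**The concern.** A crossover estimate is clean when the state in which a participant starts the second period does not depend on the drug received in the first. Here the first-period outcome is abstinence, and a person who did well in week 2 may come back to fewer cigarettes than before. If ramelteon works, that happens more often in the ramelteon-first sequence. Those participants then take placebo with a head start, and the treatment difference is diluted. For a proof-of-concept trial meant to support a Phase IIb study, the cost is a real effect that is understated or missed.

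There is also a direct route into the endpoint. A participant whose CO is still below 10 ppm in week 5 can meet the quit-Monday CO criterion with no fall in CO. The biochemical check then adds little to a self-report that carries payment. The Intake floor guards against this at study entry. Nothing comparable is stated for entry to period 2.

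**Working it through.** **Inputs from Statistical Analysis, Sample size.** "All significance levels will be set at 0.05" (sidedness is not given; two-sided is assumed). The power claim for the primary hypothesis is "Fifty subjects provide 80% power to detect a difference of 0.55 days between RAM and PLA". The variability behind that claim is given as "using a SD of 1.36 and a within-subjects correlation of 0.78". The reference mean on nicotine patch is 2.0 days. Equal sequences of 25 and 25 completers are assumed from the counterbalancing.

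**Step 1. Reproduce the stated power** (paired t-test, noncentral t, 49 df).
- If 1.36 is the SD of the within-person difference, power at 0.55 days is 80.0%. The figure reproduces.
- If 1.36 is the per-period SD with correlation 0.78, the SD of the difference is 1.36 × √(2 × (1 − 0.78)) = 0.902. Power is then 98.8% and the detectable difference 0.365 days. The figure does not reproduce.

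The first reading is used below, with the second alongside.

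**Step 2. Bias from carry-over.** Let τ be the true effect, and let λ_R and λ_P be the carry-over into period 2 after ramelteon and after placebo. The ramelteon-first sequence estimates τ − λ_R and the placebo-first sequence estimates τ + λ_P, apart from period effects that cancel. Their average is

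E[estimate] = τ − (λ_R − λ_P)/2.

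Only the difference between sequences matters. Equal carry-over gives no bias at 25/25.

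**Step 3. Tie carry-over to the mechanism.** Suppose each extra abstinent day in period 1 changes period 2 by c days. Then λ_R − λ_P = c × τ and E[estimate] = τ(1 − c/2). The documents give no value for c, so a range is assumed. Power holds the SD of the difference fixed.

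| c (assumed) | carry-over difference | expected estimate, τ = 0.55 | loss | power, SD 1.36 | power, SD 0.902 |
|---|---|---|---|---|---|
| 0 | 0 | 0.55 | 0 | 80% | 99% |
| 0.1 | 0.055 | 0.52 | 5% | 76% | 98% |
| 0.25 | 0.138 | 0.48 | 12.5% | 69% | 96% |
| 0.5 | 0.275 | 0.41 | 25% | 56% | 89% |
| −0.25 | −0.138 | 0.62 | inflated | 88% | >99% |
| −0.5 | −0.275 | 0.69 | inflated | 94% | >99% |

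A simulation of 20,000 trials per case (normal data, 25 per sequence, SD of the difference 1.36 before carry-over) gave mean estimates of 0.48 and 0.415 for c = 0.25 and 0.5. Rejection rates were 73% and 53%; they differ from the table because carry-over also changes the spread of the differences.

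**Step 4. No drug effect.** With τ = 0 the carry-over difference c × τ is zero. Simulated type I error was 4.9% to 5.1% for c = 0, 0.25 and 0.5.

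**Step 5. Carry-over common to both sequences.** With a mean of 2.0 days, c = 0.25 gives a common period-2 shift of 0.25 × 2.0 = 0.5 days. At 25/25 this causes no bias. Without a period term it raises the SD of the difference from 1.36 to √(1.36² + 0.5²) = 1.449, and power falls from 80% to 75%. If completers split 30 ramelteon-first and 20 placebo-first, the bias is (−0.5 × 30 + 0.5 × 20)/50 = −0.10 days.

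**The case against.** The strongest reply is that the design already limits the problem. Order is counterbalanced, participants are told to smoke freely in the washout, week 5 is a further week of free smoking, and CO is read three times in that week. Section 3.4 also says cigarettes are to be assessed for each day of the study. TLFB is retrospective, so at week 5 it can cover weeks 3 and 4. A reader might infer from the schedule note that washout smoking is unknown. That does not follow: what is missing is a criterion and an analytic use, not the data.

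A reader might also infer that carry-over necessarily biases the primary contrast. It does so only if it differs by first-period drug or if completer sequences are unbalanced. Nothing in the documents fixes its sign or shows how many participants would reach week 5 with low CO. Those unwilling to resume may leave, which removes some of the strongest cases as attrition.

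On the remedy, week-5 smoking follows period-1 treatment, so adjusting for it conditions on something the drug may have changed. H2a is not an exact model either: it compares the same sleep variable across weeks, whereas days abstinent has no free-smoking counterpart.

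All of this stands as a limit on size and certainty. None of it supplies a definition of resumption, a check at week 5, or a use of baseline smoking in H1.

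**Conclusion.** The point holds as a conditional one. Resumption is required but neither defined nor verified, and H1 sets aside smoking data that the trial collects in both baseline weeks. If ramelteon works and period-1 success carries forward at c = 0.1 to 0.5, a 0.55-day effect is estimated as about 0.52 to 0.41 days. Power falls from 80% to between 76% and 56% on the SD reading that reproduces the plan's figure. These sizes rest on an assumed c, a fixed SD and balanced sequences.

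Two stronger readings are not supported. The first is a false-positive risk: carry-over acting through period-1 abstinence vanishes when the drug has no effect. The second is a loss of half the target effect: that needs a carry-over difference of 0.55 days, or c = 1, so that every extra day in week 2 is repeated in full in week 6.

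**What to change.** Keep the unadjusted H1 contrast and pre-specify beside it:

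- **(a)** an H1 model with a period term and each period's own baseline cigarettes per day and mean CO (week 1 or week 5), described as a partial remedy because week-5 values follow period-1 treatment;
- **(b)** week-1 and week-5 CO and cigarettes per day, with TLFB covering weeks 3 and 4, reported by sequence;
- **(c)** a sensitivity analysis flagging participants whose week-5 CO is below the 10 ppm Intake level.

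The sponsor should reconcile the resumption requirement in the Washout Weeks paragraph with the absence of any check at week 5. A CO threshold for starting period 2, with rescheduling when it is missed, is not recommended here. If ramelteon works, ramelteon-first participants would miss it more often, and washout length would then depend on treatment.

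The cost is analysis wording, one or two degrees of freedom for the baseline terms and one for period, and a little more reporting. No new measurement is needed. A period-1-only comparison is a poor substitute: at 25 versus 25 its power for 0.55 days is about 30% with a per-period SD of 1.36.
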